4.2 STATISTICAL DECISION RULES

Incidence rates of the primary and secondary endpoints will be calculated with a 95% Confidence interval (CI). The HR from Cox proportional hazard regression models will be used for comparison of event rates of the primary and secondary endpoints in each exposure (treatment) cohort. Statistical two-sided tests will be used with a significance level of 0.05.

Multiple Comparisons/ Multiplicity

No adjustments for multiple comparisons or multiplicity are planned among endpoints for this Post Authorization Safety Study.

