- Previous history of major lower extremity (hip, knee) arthroplasty, arthroscopic surgery (information on arthroscopic surgery not available in Italian database)
- General surgery, major orthopedic surgery (<1month prior to incidence of VTE)
- (Information on general surgery not available in Italian database)
- Multiple trauma (<1month prior to incidence of VTE)
- Hip, pelvis, or leg fracture (<1month prior to incidence of VTE)
- Stroke (<1month prior to incidence of VTE)
- Acute spinal cord injury (paralysis) (<1month prior to incidence of VTE)
- Hormone replacement therapy (limited information available in both databases)

A Cox model will be used in order to take into account the time varying component. The time from the beginning of the treatment (one among three types, BZA, raloxifene, and bisphosphonate) to the occurrence of primary end point is fitted in this model. The Proportional Hazards (PH) assumption will be tested for each covariable. If the PH assumption does not hold for some covariates, the use of time-varying HR for those covariates will be explored. If a categorical variable with more than 2 levels does not satisfy this PH assumption, collapsing some categories will be attempted to satisfy the PH assumption. Correlations between variables will also be evaluated in order to find independent factors and a final model that is clinically relevant.

First, the univariate analysis will be carried out on each covariable in order to determine the explanatory variables to be included in the final multivariate model. All significant variables with a p -value ≤ 0.20 in the univariate model will be taken into account in the multivariate Cox model.

If > 80% of the important risk factors for VTE listed above does not satisfy the PH assumption, a logistic regression analysis would be performed instead of Cox model to otherwise determine if the covariable is related to the incidence primary endpoint (VTE). The dependent variable would be the incidence of the primary end point during the follow-up period categorized as a binary variable. The 2 indicators of treatment group (BZA vs. bisphosphonates, raloxifene, will be forced in the multivariate model (Cox model or logistic model) to analyze incidence in each class of treatment, adjusted on

significant factors. Hazard ratios (HR) (odds ratios (OR) in case of logistic regression) with 95% Confidence intervals (CIs) and p-values will be presented.

[figure not shown]
Patients Switching Medications

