In this study the proportion and demographic and clinical characteristics of patients that switch medications between the study drugs will be reported alongside patients that do not switch medications. Both the AT and CR analytic approaches will be used for all study endpoints and the results reported. In the CR method, if a patient switches from one exposure (study drug) cohort group to another, they will have several treatment durations and will belong to multiple cohort groups but will be analyzed according to their original exposure cohort group (i.e., CR/intent to treat approach). In the AT approach, all exposure cohort groups will be included as a time-dependent variable. With the exposure cohort group as a time-dependent variable, each event will be assigned to the treatment being taken at the time of occurrence. The duration of treatment for each cohort group will be from the date of the first prescription to the date of the event or to the end of treatment, whichever occurs first. The covariates of patients that switched treatment at the time of the event or at the end of follow-up would be considered in this model.

[figure not shown]
The following diagrams shows some example of calculating duration for patients with switched treatments with both the AT and CR approaches.

Figure 2a. Calculating the duration of treatment for patients that switched treatment using the as-treated (AT) approach.

A, B, C: Treatment cohort types. X= Incidence date of primary end point

Figure 2b. Calculating the duration of treatment for patients that switched treatments using the cumulative risk (CR) approach.

A, B, C: Treatment cohort types. X= Incidence date of primary end point

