8.2 STATISTICAL ANALYSES

8.2.1 PATIENT CHARACTERISTICS

Descriptive statistics on available patient characteristics (e.g. age, BMI, smoking, history of relevant medical diagnoses) will be reported for all exposure groups at index date. A summary table will present and compare all the patients' demographic data at index date (BZA/raloxifene/bisphosphonates).

- Age (years): derived by difference between the year of time of interest and year of birth.
- Weight (kg): recorded at the given date, or if not available, at the most recent date before or it
- Height (cm): the value at the given date or, if not available, at the most recent date before or after it.

- Body Mass Index (BMI) (kg/m^2), calculated from weight and height as defined previously. BMI will be described in quantitative measure and in categorical data, as usual
- Alcohol use
- Smoking status
- Time since diagnosis of osteoporosis: derived by the difference between the index date and the diagnosis date.
- Previous treatment for osteoporosis (before index date) (yes versus no) or Number of different treatments for osteoporosis in the entire patient history available
- Previous history of VTE (Venous Thromboembolic Events) (before index date)
- Previous history of major lower extremity (hip, knee) arthroplasty, arthroscopic surgery (information on arthroscopic surgery not available in Italian database)
- General surgery, major orthopedic surgery (<1month prior to incidence of VTE) (information on general surgery not available in Italian database)
- Multiple trauma, (<1month prior to incidence of VTE)
- Hip, pelvis, or leg fracture (<1month prior to incidence of VTE)
- Stroke (<1month prior to incidence of VTE)
- Acute spinal cord injury (paralysis) (<1month prior to incidence of VTE)
- Hormone replacement therapy (limited information available in both databases)

If the diagnoses for any of the conditions listed in this section (8.2.1) are not found in the database, they will be assumed to be absent.

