8.2.4 TIME TO EVENT ANALYSIS

Time to event analysis will be conducted as a secondary analysis and the following factors possibly related to incidence of end points will be considered at the date of Incidence or the last visit before incidence: age, BMI, smoking (depending on availability of data), history of diabetes, history of hypertension, history of malignancies, history of VTE, and some other co-morbidities. Univariate Cox models (if applicable, depending on the PH assumptions for each factor, otherwise logistic regression model) will be performed for each factor and then, the analysis will be complemented by a multivariate Cox model (if applicable, depending on the PH assumptions for each factor) or a logistic regression. Hazard ratios (HR) or odds-ratios with 95% CI and p-values will be presented for significant factors at the 0.05 level.

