8.2.5 SUMMARY OF STATISTICAL ANALYSIS

Analyses for Primary Objective and Secondary Objective 1

Comparator: BZA vs. bisphosphonate (primary objective), BZA vs. raloxifene (secondary objective 1).

Study endpoint: VTE.

Populations: a. Full BZA full raloxifene, random age stratified bisphosphonate subgroup
b. Incident user subgroup.

Statistical Method:

- i. Incidence rate, cumulative method (*Total new cases during follow-up period / Total persons at risk during follow-up period*) with stratification by risks of interest e.g. Age, BMI.
- ii. Univariate and multivariate incidence rate by incidence density (*Total new cases during follow up period / Total person years during follow-up period*)*1000) method using Cox regression model and a Likelihood Ratio Test for testing Hazard Ratio (HR) =1 (ratio of hazard in BZA population vs. bisphosphonate/raloxifene population) with covariates associated with VTE outcome and exposure (Drug groups).

Sensitivity analyses:

- i. Repeat analysis will be conducted that compares using a 30-day and a 90-day definition of recent exposure with using the 60-day definition.
- ii. Missing Data: First, the analyses will be repeated utilizing a complete dataset in which cases with missing values of main study covariates of BMI, smoking status and alcohol status have been deleted. Second, multiple imputation for the missing values of BMI, smoking status, alcohol status will be used in the second set of analyses.

Multiple imputation procedure:

- 1) Estimate distribution of BMI, smoking status and alcohol status according to patients whose data are available.
- 2) For the patients who had missing values those variables draw values of the variables from the distribution from 1).
- 3) With the imputed dataset (including none-missing data), estimate HR as described.
- 4) Repeat 2)-3) for m times, and record HR of each time.
- 5) Calculate mean of m estimates of HR.
- 6) Adjust variance of HR with the following formula, and use the variance to calculate confidence interval.

$$V = \left(1 + \frac{1}{M}\right) V_B + V_W.$$

V_B is the between imputation variance, and V_W is within imputation variance.

Analyses for Secondary Objective 2 and Secondary Objective 3

Comparator: BZA vs. bisphosphonate (secondary objective 2), BZA vs. raloxifene (secondary objective 3).

Study endpoint: Secondary endpoints.

Population: a. Full BZA, full raloxifene, random age stratified bisphosphonate subgroup.
b. Incident user subgroup

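### Five VTE risk factors are dated by the VTE itself, with no rule for women without VTE; coded as written, they can pull the adjusted hazard ratio toward 1

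*SAP*

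**What the plan says.** SAP 8.1.4 (Time to Event Analysis) lists factors to be considered for the Cox model. Five are tied to the month before the VTE: "General surgery, major orthopedic surgery (<1month prior to incidence of VTE"), multiple trauma, hip/pelvis/leg fracture, stroke, and acute spinal cord injury.

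Other statements bear on timing and entry:

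- **SAP 8.2.4:** "factors possibly related to incidence of end points will be considered at the date of Incidence or the last visit before incidence". This date again exists only for cases.
- **SAP 8.1.4, model sentence:** "A Cox model will be used in order to take into account the time varying component". It does not name these five items.
- **SAP 8.1.4, Patients Switching Medications:** covariates "at the time of the event or at the end of follow-up would be considered in this model". This covers only women who switched.
- **SAP 8.2.1:** the same five items appear among characteristics that "will be reported for all exposure groups at index date", and conditions not found are taken as absent.
- **SAP 8.1.4, entry:** the model is to control imbalances seen in the baseline description. In addition, factors with p ≤ 0.20 "in the univariate model will be taken into account in the multivariate Cox model".
- **SAP 8.2.5:** the multivariate model is run "with covariates associated with VTE outcome and exposure (Drug groups"), with no threshold for the association with drug group.
- **SAP 4.2:** "The HR from Cox proportional hazard regression models will be used for comparison of event rates" between cohorts.

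**The concern.** A woman without VTE has no month before her VTE. With absence as the default, she is coded 0 on all five items whatever surgery, fracture or stroke she had. A positive value then implies that the woman is a case, so the covariate is partly the outcome.

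Adjusting for such a variable does not control confounding. Within the positive group every woman has the event, so those cases carry almost no information on whether treatment changes risk. They pull the pooled HR toward 1. In a post-authorization safety study of an identified VTE risk, a real excess would be understated. The items' own HRs would also be reported and would be grossly inflated.

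**Working it through.** **Inputs.** From SAP 5.4: 1,823 bazedoxifene and 10,938 bisphosphonate women (12,761 in total). From protocol 7.1: comparator VTE rate 1.74/1000 PY and 15% annual loss. Follow-up is 5 years. The share q of VTEs with a recorded trigger is not in the documents, so a range is shown.

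**Scale.** The plan gives no figure for this item, so protocol Table 3 was reproduced as a check on the inputs. For the 1:6 row at IRR 2, with 5 × 0.85 = 4.25 PY per woman (inferred, not stated):
- d1 = 1,750 × 4.25 × 0.00348 = 25.9 and d0 = 10,500 × 4.25 × 0.00174 = 77.7
- SE = √(1/25.9 + 1/77.7) = 0.227
- 2 × exp(±1.96 × 0.227) = 1.28 to 3.12, against the printed 1.3 to 3.1

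The simulations instead apply the loss continuously, giving 3.42 PY per woman. At HR 2 the expected events are 10,938 × 3.42 × 0.00174 + 1,823 × 3.42 × 0.00348 = 65.1 + 21.7, about 87.

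**Does the screen stop these items?** With no positives among non-cases, one positive among d cases has Fisher p = d/12,761. That is 0.005 for d = 60, 0.007 for d = 87 and 0.008 for d = 100. A single positive case therefore passes p ≤ 0.20 on an exact or likelihood-ratio test; a Wald screen could behave differently under near-separation. The odds ratio is infinite, so the logistic fallback has no finite estimate for the item.

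**Size, true HR 2, equal q in both arms.** If triggered cases contribute a log HR near 0, the adjusted HR is roughly 2^(1−q). The simulation used 400 replicates per scenario. Triggered cases were split over the five items 40/10/30/15/5% (assumed), and items were screened and then entered with treatment.

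| q | 5% | 10% | 30% | 50% |
|---|---|---|---|---|
| 2^(1−q) | 1.93 | 1.87 | 1.62 | 1.41 |
| Unadjusted HR | 1.98 | 1.96 | 1.94 | 1.96 |
| Case-only items, p ≤ 0.20 screen | 1.96 | 1.90 | 1.63 | 1.44 |
| Also associated with drug group, p ≤ 0.20 | 1.92 | 1.85 | 1.63 | 1.48 |
| Also associated with drug group, p ≤ 0.05 | 1.97 | 1.93 | 1.77 | 1.68 |
| Significant, unadjusted (%) | 74 | 75 | 72 | 73 |
| Significant, case-only, p ≤ 0.20 screen (%) | 72 | 71 | 49 | 30 |

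A separate simulation with all five items forced in gave 1.86 at q = 10% and 1.62 at 30%.

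If the flag is instead switched on only at the case's own event time, nobody else in the risk set is positive. Triggered cases then drop out of the comparison. The HR is nearly unbiased (1.98/1.96/1.91/1.96), but significant results fall to 72/73/61/50%.

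**True HR 1, equal q of 30%.** Unadjusted 0.99, case-only 1.00. There is no systematic shift, although in single datasets the log HR differed from time-updated coding with an SD of 0.10 to 0.20.

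**The same rule for every woman.** Triggers were simulated as random events with a 30-day window and a 30-fold hazard (assumed), true HR 2, q = 10% and 30%:
- time-updated coding: 1.93 and 1.99
- end-of-follow-up anchor: 1.91 and 1.97
- case-only coding, one pooled item: 1.80 and 1.62

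In a further set with true trigger hazard ratios of 20 to 40, case-only coding returned covariate HRs of about 250 to 390. Time-updated coding returned about 19 to 42.

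**The case against.** **The SAP does not commit to case-only coding.** The time-varying sentence and the end-of-follow-up anchor point toward readings that do little harm. That is fair: a careful analyst could code the items sensibly. But the first is not tied to these items and the second covers switchers only. Where the SAP wants a time-dependent variable, as for exposure group, it says so.

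**Adjustment is tied to baseline imbalance, which would keep these items out.** This does not rescue the plan, because 8.2.1 places the same five items in the index-date list, and the p ≤ 0.20 rule admits them in any case.

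**A reader might infer that any HR adjusted for these items is uninterpretable.** The figures do not support that. SAP 2.1 says hospital information is not systematically collected, so the recorded share may be low, and at 5–10% the shift is small. If association with drug group is also required at p ≤ 0.05, an average of only 0.06 to 0.12 items enter at those shares.

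**A reader might also infer that the rule creates a false signal when there is no effect.** Simulation can show this: with 10% triggered in bazedoxifene and 30% in bisphosphonate at equal overall rates, the HR moves from 0.95 to 1.21. But those shares imply rate ratios of 0.9/0.7 = 1.29 for untriggered and 0.1/0.3 = 0.33 for triggered VTE, which are opposite drug associations. Reversing the shares gives 0.7/0.9 = 0.78 and 0.3/0.1 = 3.0, and the HR moves from 1.00 to 0.80. Nothing in the documents suggests such a pattern. When shares differ only through trigger rates and the drug effect is constant, case-only coding gives 1.00 and 0.92 against 0.98 and 0.93 time-updated, so there is no extra distortion.

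**Containment.** SAP 8.1.2 makes cumulative incidence primary and 8.2.4 calls time-to-event secondary. Neither crude rates nor the univariate HR is touched, so a shift would be visible beside them. This stands and limits the severity.

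**Conclusion.** The point holds and should be fixed. The timing rule as written is undefined for most of the cohort and, followed literally, makes five covariates depend on the outcome. The p ≤ 0.20 screen then favours their entry into an adjusted HR that the SAP may use to compare cohorts.

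With equal trigger shares and a real effect, the bias is toward 1. At a true HR of 2 it is small for recorded shares of 5–10% and material at 30% (about 1.63 against 1.94, with significant results falling from 72% to 49%). With equal shares and no effect there is no systematic shift. At a true HR of 1, a shift needs drug associations in opposite directions for triggered and untriggered VTE. These sizes rest on an assumed trigger share, an assumed split over the items, and the literal coding. The gap in definition does not depend on any of them.

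**What to change.** In SAP 8.1.4, define the five items for all women by one rule. In the main multivariate model, use only values dated on or before the index date, with a stated look-back (the inclusion criteria guarantee only six months of history). Apply that rule in the baseline-imbalance sentence, the covariate list and the switching paragraph of 8.1.4, and in 8.2.4 and 8.2.5. Remove the VTE-based dating from the index-date list in 8.2.1.

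If recent triggers are also wanted, add a sensitivity analysis with a time-dependent indicator: event recorded in the preceding 30 days, updated at each event time for every woman at risk. State its limits:
- Clinical fractures and ischemic stroke are secondary endpoints (SAP 6.2), so post-index values may lie on the causal path.
- Hospital events reach the GP file only at later visits (SAP 2.1), so dates may be too imprecise for a 30-day window.
- General surgery is not available in the Italian database (SAP 8.1.4).

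The cost is SAP wording plus modest counting-process programming for the sensitivity analysis; no new data source is needed. The downside is that the main model will not control for triggers after the index date.

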5.4 SUBGROUPS

Age stratified randomly selected subgroup

In the current dataset, there are 1,823 patients in the bazedoxifene group and 82,041 patients in the bisphosphonate group. This means that there is more than 40 times the number of subjects in the bisphosphonate group compared to the number of subjects in the bazedoxifene group. To limit the number of patients in the bisphosphonate group, an age stratified random subgroup will be selected. Based on the sample size and relative risk estimates provided in the final study protocol (study protocol section 7.1, Sample size calculation), the 1,823 bazedoxifene subjects will be adequately matched by a ratio of 1:6 bisphosphonate subjects. Therefore $1,823 \times 6 = 10,938$ bisphosphonate treated subjects are needed to be randomly selected from the total of 82,041 bisphosphonate treated subjects.

Selection scheme: The age of subjects in the study will be categorized into 4 groups (45-49, 50-59, 60-69, and ≥ 70). In the bisphosphonate group, the percentage of subjects in each of these age groups is 1.4%, 13.7%, 28.7%, and 56.2% respectively. To maintain the same proportion of subjects in each age group for the bisphosphonate subgroup, there will be $1.4\% \times 10,938 = 153$ bisphosphonate treated subjects randomly selected from the 45-49 age group; $13.7\% \times 10,938 = 1,499$ subjects randomly selected from the 50-59 age group; $28.7\% \times 10,938 = 3,139$ subjects randomly selected from the 60-69 age group; $56.2\% \times 10,938 = 6,147$ subjects randomly selected from ≥ 70 age group.

Incident cases of study endpoints

Women with a history of study end points recorded prior to the index prescription will not be included in the analysis for that specific outcome, but will be analyzed separately as subgroups for each study end point. The analyses of the primary and secondary endpoints will be performed using these incident cases of study endpoints subgroups.

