7 HANDLING OF MISSING VALUES

For each variable, the number and proportion of patients missing data for each treatment group will be specified. The primary analyses will be done using only the information available in the unmodified dataset. Smoking status, alcohol consumption, height and/or weight (BMI) values are known to be missing for approximately 40-60% patients in the Cegedim LPD based on previous studies. (Age of patients will always be known as it is a selection criterion). Dates are automatically recorded in the Cegedim LPD and doctors can select diseases codes from the pre-defined lists. In all analyses, if a condition (disease or treatment) other than the diagnosis of osteoporosis is not recorded, it will be assumed to be non-existent.

To estimate the effect of missing data, two additional analyses for the primary study endpoint will be conducted. First, the analyses will be repeated utilizing a dataset in which cases with missing values of main study covariates of BMI, smoking status and alcohol status are excluded. The disadvantage to this approach is the reduction in the sample size. Another disadvantage to this approach is that the subjects with missing values may be different than the subjects without missing values (e.g., missing values that are not missing at random), resulting in a non-representative sample after removing the cases with missing values. Second, multiple imputations for the missing values of BMI, smoking status, alcohol status will be used in the second set of analyses and compared to complete case analyses to understand the potential impact of missing data on results [2].

Outlier

Extreme values for weight and height will be searched for. If a value seems implausible, as regard to gender or ratio weight/height, it will be put as missing.

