8 STATISTICAL METHODOLOGY AND STATISTICAL ANALYSES

8.1 STATISTICAL METHODS

Analyses will be conducted separately for each country and the final report will consist of three parts: one part for Italy, one part for Spain, and the final part with pooled data of both countries. Pooling of data for the combined results of Italy and Spain will be done at the patient level. ICD9 codes of the Italian data will be mapped unto ICPE codes of the data from Spain. ICD9 codes that do not map directly to ICPE will be noted and the frequency of patients with outcomes in these unmapped categories will be reported. Given the very low enrolment from Italy (approximately 40 patients, vs. approximately 1700 from Spain) very few patients/outcomes from Italy are likely to be reported as unmapped. Assessment and adjustment for confounding will be done separately for each country and also done separately for the pooled analyses and follow the same methodology in the individual and pooled analyses. All statistical analyses will be performed using the SAS software 9.2, running with SAS Enterprise Guide 4.3, on a Windows Server.

The qualitative variables will be described by using usual statistics: population size and percentages (relative to the non-missing data) for each modality. Quantitative variables will be described with the number of observed data, mean, standard deviation (SD), median, and ranges. Two-sided 95% confidence intervals will be presented for relevant variables.

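### General and arthroscopic surgery, which the Italian database does not hold, are coded absent for every Italian woman in the pooled VTE model; if comparators are more Italian than BZA users, this coding alone would lower the adjusted BZA hazard ratio

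*SAP*

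**What the plan says.** The covariate list in SAP 8.1.4 includes previous lower-extremity arthroplasty and arthroscopic surgery, with the remark "information on arthroscopic surgery not available in Italian database". It also includes general surgery and major orthopaedic surgery in the month before VTE, with the remark "Information on general surgery not available in Italian database". SAP 8.2.1 repeats both. Arthroplasty and major orthopaedic surgery carry no such remark.

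Two rules then decide the coding. SAP 8.2.1 says that listed conditions whose diagnoses "are not found in the database, they will be assumed to be absent". SAP 7 says of all analyses that "if a condition (disease or treatment) other than the diagnosis of osteoporosis is not recorded, it will be assumed to be non-existent". Neither makes an exception for an item that one country's database lacks altogether.

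SAP 8.1 states: "Pooling of data for the combined results of Italy and Spain will be done at the patient level". It applies the same confounder methodology to the country and pooled analyses. Country is not among the covariates listed in 8.1.4.

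On numbers, SAP 8.1 describes low Italian enrolment as "approximately 40 patients, vs. approximately 1700 from Spain", and SAP 5.4 states that "there are 1,823 patients in the bazedoxifene group and 82,041 patients in the bisphosphonate group". The 1:6 bisphosphonate sample in 5.4 is stratified by age only.

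**The concern.** A field that does not exist is not the same as a diagnosis that a GP did not enter. Coding it as a clinical no is an error that follows country, and country appears to be strongly tied to treatment arm.

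In Spanish women, VTE after general or arthroscopic surgery can be attributed to the surgery term. In Italian women the same events stay in the no-surgery reference rate. If the comparator is much more Italian than the BZA group, that reference rate is inflated mainly in the comparator. The adjusted BZA hazard ratio then falls, in a study set up to characterise VTE harm. Protocol Table 3 puts the lower confidence limit at only 0.9 to 1.0 for a true rate ratio of 1.5, so there is little room for an avoidable loss.

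**Working it through.** **Inputs from the documents.** The documents give no figure for this bias. The comparator sample does reproduce: 1,823 × 6 = 10,938, and 153 + 1,499 + 3,139 + 6,147 = 10,938 (SAP 5.4).
- Spanish share of BZA: 1,700 / (1,700 + 40) = 97.7%. SAP 8.1 says enrolment, not BZA. It can only be BZA, because the bisphosphonate group alone is 82,041.
- Comparator VTE rate 1.74 per 1,000 PY and 15% annual loss (protocol 7.1). Five-year follow-up then gives (1 − 0.85⁵) / (−ln 0.85) = 3.42 PY per woman.
- Panel sizes: Italy 800,000 and Spain 320,000 (SAP 2.1), so 800 / 1,120 = 71% Italian.

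**Assumptions.** The comparator is 71% Italian, varied below. The one-month surgery item covers 0.2–0.4% of person-time and multiplies the VTE rate by 10–40. Surgery frequency is the same in both arms and countries. True HR is 1.50.

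**Is a mostly Spanish comparator plausible?** At 97.7% Spanish, 0.977 × 82,041 = 80,154 women, or 25% of the 320,000 patients of both sexes and all ages seen yearly in Spain. At 50%, 41,020 women would be 12.8% of the Spanish panel and 5.1% of the Italian one. A more Italian comparator looks likely. This is not proof: the panel figure is annual, while accrual ran 36–43 months.

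**Hand check** (p = 0.4% of person-time, RR = 20). With Spanish share s, the VTE rate among women recorded as no surgery, relative to the true no-surgery rate, is

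[s(1 − p) + (1 − s)(1 − p + p·RR)] / [s(1 − p) + (1 − s)]

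- BZA, s = 0.977: (0.9731 + 0.023 × 1.076) / (0.9731 + 0.023) = 1.002
- Comparator, s = 0.286: (0.2849 + 0.714 × 1.076) / (0.2849 + 0.714) = 1.054
- HR ≈ 1.50 × 1.002 / 1.054 = 1.43

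**Model.** A Poisson model with treatment and recorded surgery, fitted to expected counts (equivalent to a constant-hazard Cox model), at 71% Italian comparators:

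| Person-time after surgery | RR | Adjusted HR (true 1.50) |
|---|---|---|
| 0.2% | 10 | 1.48 |
| 0.4% | 10 | 1.46 |
| 0.4% | 20 | 1.43 |
| 0.4% | 40 | 1.37 |

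Variations on the 0.4%, RR 20 case:
- Comparator 90%, 50%, 25% or 2.3% Italian: 1.41, 1.45, 1.48, 1.50.
- Half of the relevant surgery still visible in Italy: 1.46.
- Country term added: 1.50.

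**Country difference in baseline VTE** (same case, Spain:Italy rate ratio assumed):

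| Spain:Italy | Coded as planned | Surgery terms dropped, no country term | Country term added |
|---|---|---|---|
| 0.7 | 1.11 | 1.16 | 1.50 |
| 1.3 | 1.69 | 1.79 | 1.50 |

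Dropping the surgery terms removes the coding error but leaves confounding by country. A country term deals with both.

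**The case against.** Several points on the other side stand.
- Only two sub-items are missing in Italy. Arthroplasty, major orthopaedic surgery, leg fracture and multiple trauma carry no such note. A reader might infer that surgery as a whole is visible only in Spanish women; the documents do not say that.
- A reader might model surgery as a fixed characteristic of 5–10% of women with a rate ratio of 3–5, which takes a true 1.50 to between 1.41 and 1.25. That does not fit general surgery, which is a one-month item: 10% of person-time within a month of surgery would need about 1.2 operations per woman per year. Arthroscopic surgery is a history item, but the documents give no basis for such figures.
- The comparator's country mix is not stated. If it matches BZA, there is no bias.
- Covariates are only considered, and enter at univariate p ≤ 0.20.
- SAP 8.1 already plans a Spain-only analysis, which this coding does not touch. SAP 8.1.1 has the availability of medical history checked in both databases.
- The shift is small against sampling error. With 1,823 × 3.42 × 0.00174 × 1.5 ≈ 16 BZA and 10,938 × 3.42 × 0.00174 ≈ 65 comparator events, the log-HR standard error is √(1/16.3 + 1/65.1) ≈ 0.28. A move from 1.50 to 1.43 is about 0.17 of that.

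These limit the size and certainty. They do not make the coding valid. The SAP does not name the Spain-only model as the reference for surgery adjustment, and checking availability does not alter the absent rule. SAP 8.2.4 calls the time-to-event analysis secondary, but SAP 4.2 uses its hazard ratio to compare the cohorts.

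**Conclusion.** The coding rule is wrong as written for general and arthroscopic surgery in the pooled VTE model, and should be fixed. On its own it is expected to lower the pooled adjusted BZA hazard ratio, from a true 1.50 to about 1.48 to 1.37 under the one-month inputs and 71% Italian comparators. That direction rests on three conditions: the SAP 8.1 split refers to BZA users, the comparator is substantially more Italian, and the term passes the p ≤ 0.20 screen. The shift shrinks as the comparator becomes more Spanish and vanishes when the mixes match.

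A reader might infer that the pooled result is certain to be pulled towards or below 1. The documents do not support that. The coding alone takes the estimate below 1 only if the true ratio is close to 1. A baseline country difference in VTE recording, for which no figure is given, could move the net estimate either way.

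**What to change.** In SAP 7, 8.1, 8.1.4 and 8.2.1:
1. Limit the absent rule to variables that the country's database collects. Treat the others as not available in that country.
2. Use general and arthroscopic surgery only in the Spain model and leave them out of the Italian and pooled models; or keep them in the pooled model only with a country term.
3. In either case, stratify the pooled Cox model by country.
4. Report the country split of each cohort, and the Spain-only BZA hazard ratio with and without these two covariates.

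The cost is SAP wording and one or two extra model runs. The stratified pooled estimate will rest mostly on Spanish data: about 40 Italian BZA women give only 40 × 3.42 × 0.00174 × 1.5 ≈ 0.4 expected VTE events at a true ratio of 1.5, so little comparative information is lost.
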